## **Severity**

- The most serious risk in the proposed research is any adverse outcome that may jeopardize the welfare of participants or caregivers. Possible adverse events that are anticipated include an unintentional disclosure of personal health information to an unauthorized individual. Additionally, it is possible that during the tele-health mediated assessment phase of this project, the individual or their caregiver could conceivably experience an acute medical event requiring immediate medical attention. In the unlikely event that this were to occur, the study staff would assist the participant or their caregiver in alerting local EMS, or alternatively would contact local EMS on their behalf.

## **Expectedness**

- AEs that are unanticipated will be reported immediately to the Washington University in St. Louis IRB by the PI. The IRB will determine whether it is appropriate to stop the study protocol temporarily or will provide suggestions/modifications to the study procedures. Possible modifications include adding these possible adverse events to the consent form and re-consenting all study participants. The PI will be responsible for monitoring participant safety on a monthly basis at regularly scheduled research meetings. The PI will keep a written log of all adverse events and ensure that the IRB is contacted immediately. The PI will also keep a log of the outcome of IRB decisions regarding adverse events and enforce any changes that need to occur as a result of the IRB decisions. If the preliminary outcome data indicates harmful impact of the program to caregivers or their families, the Washington University in St. Louis committee will be notified and it is possible that the study will be discontinued.

## **Data Collection Procedures for Adverse Events**

- The PI will be responsible for monitoring participant safety on a monthly basis at regularly scheduled research meetings. The PI will keep a written log of all adverse events and ensure that the IRB is contacted immediately and will also keep a log of the outcome of IRB decisions regarding adverse events and enforce any changes that need to occur as a result of the IRB decisions. If the preliminary outcome data indicates harmful impact of the program to caregivers or their families, the Washington University in St. Louis committee will be notified and it is possible that the study will be discontinued.

## **Reporting Procedures**

- The PI will be responsible for monitoring participant safety on a weekly basis. He will be informed of any adverse events (AE) as soon as they occur, and he will report them to the Washington University in St. Louis IRB within 24 hours of becoming aware of the event. The IRB will determine whether it is appropriate to stop the study protocol temporarily or will provide suggestions/modifications to the study procedures. Possible modifications include adding these possible adverse events to the consent form and re-consenting all study participants. Because this study takes place at 13 sites, the PI will also be responsible for notifying all other site's PI's.
- Additionally, in accordance with NIH policy, the PI will notify the study's NIH program officer within 10 business days of the study team becoming aware of an unexpected serious adverse event (SAE). For all AEs or serious adverse events (SAE) that are either expected or unrelated to the study, the PI will provide a summary to the study's NICHD program officer with the annual progress report.

## **Adverse Event Reporting Period**

AE reporting to the Washington University in St. Louis IRB will occur within 24 hours of becoming aware of the event. Additionally, in accordance with NICHD policy, the PI will notify the study's NICHD program officer within 10 business days of the study team becoming aware of an unexpected serious adverse event (SAE).

## **Post-study Adverse Event**

There are no anticipated post-study adverse events that would accrue from cross-referencing or analysis of research data since this information will not be returned to the family.

## **EXPECTED RISKS/ BENEFITS:**

### **Potential Risks**

- There is always a risk of loss of privacy and loss of confidentiality, however the study team will do the following to make sure risk remains minimal:
  - Data will be maintained on password-protected secure networks at each site.
  - Only investigators and approved study staff will have access to identified data.
  - Any unplanned events or breaches in data security will be reported to the WU HRPO office.
  - In the unlikely event of a breach of genetic data, the data are protected under the Genetic Information Nondiscrimination Act of 2008 (GINA), which makes it illegal for health insurance companies, group health plans, and most employers to discriminate based on genetic information.
  - There is the risk that a participant or caregiver may feel uncomfortable answering study questions. Participants may leave blank any questions they prefer not to answer.

### **Benefits**

The societal benefit of this study this text-based intervention can be translated to other clinical or community-based settings to reduce obesity and diabetes risk among patients with a psychiatric condition.

### Funding Source and Conflicts of Interest

This protocol is funded by the National Institutes of Health in the amount of \$647,025. There are no conflicts of interest.

Informed Consent Cover page

Title: Adaptation of an Evidence-based Interactive Obesity Treatment Approach (iOTA) for Obesity Prevention in Early Serious Mental Illness: iOTA-eSMI.

NCT Number: NCT03980743

Date: October 19, 2020

Analytic plan

RFA-MH-18-706 specifies goals of the R34 mechanism include assessment of feasibility, acceptability, tolerability, and target engagement. Thus, statistical testing of short- or long-term effects, estimation of effect size, or definitive subgroup analyses are not within the scope of the RFA. We have chosen a 2:1 randomization ratio with a total sample of 60 subjects so as to increase precision in understanding the dynamics of the active intervention. Differences between the active intervention and the control groups will be explored to inform the design of the resulting future clinical trial, which is planned as an R01 application following the completion of the proposed pilot study. The primary outcome for the present study will be weight change. Within the active iOTA treatment group, we will use analysis of the process variables to refine the intervention and plan what outcome measures are appropriate for understanding the intervention's effectiveness. In addition, potentially relevant biological variables, such as gender, age, race and ethnicity will be explored in the analysis of the pilot study through our recruitment of a diverse sample, and though our planned exploration of the effect of these variable on outcomes in the analysis.

Planned primary and secondary analysis: In addition to the use of change in body weight from baseline as the primary outcome for this pilot study, secondary outcomes will include change in BMI, psychophysical skills and related self-efficacy. Weight/BMI will be measured at each visit (up to 10 visits over 9 months); we will use a repeated-measures mixed model to look at trajectory over study course with a time x treatment interaction estimating the treatment effect. Increase in self-efficacy for diet and exercise is the proposed mechanism of action for the active iOTA intervention. Measures of Psychophysical Awareness will be measured at every visit (total of 5 time points). Trajectory of self-efficacy scores will be compared between treatment groups. Finally, we will use structural equation growth models to estimate the correlation between the trajectory of psychophysical skills and related self-efficacy and that of weight/BMI.

Exploratory analyses: will focus on characterizing feasibility, engagement and implementation challenges as measured by i) enrollment, retention and visit adherence, ii) obesity intervention acceptability,^{26,27} iii) text response rates, iv) client expectations,²⁸ v) fidelity and vi) client and staff-rated feasibility, appropriateness, acceptability, and vii) staff burden, including evaluation of how these variables impact effectiveness with respect to BMI and self-efficacy. Exploratory analyses will also evaluate how mental health self-efficacy and psychotropic medication compliance impact iOTA treatment compliance/engagement.

Data Management All data will be entered into the electronic database REDCap via a secure WUSM web portal and stored on secure WUSM servers, which can be accessed securely through the WU or FAU networks. The database management is built with multiple layers of security and follows best practices and WUSM requirements for securing sensitive data. The iOTA program will be monitored through a secure web-portal via the WU network. All automatic system generated messages in the iOTA program will be sent directly to subjects' mobile phones through an online application developed and supported by technology vendor, Integrity, who has existing WU IRB and Information Security office approval for involvement with the parent iOTA program. The research team will use the iOTA online web portal from WU computers on the WU network. Integrity captures/stores all text messaging data (data sent to participants and received back from participants) and transmits the data to the WU research team using the REDCap API via a secure WUSM web portal stored on secure WUSM servers.

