***Study Participants*** Aim 3 will include a randomized 24-week pilot study of the adapted intervention, followed by 12 weeks of text messaging intervention alone in 60 participants (30 at each study site). Participants will be CMHC clients aged 18-45 with eSMI receiving mental health services at each clinical site, and will be randomized 2:1, iOTA-eSMI intervention: health education control. Groups will be balanced to reflect the age, gender, racial and ethnic distribution of the client-base at each site. Targeted group size for this pilot study will permit exploration of treatment group interactions with age and with racial/ethnic differences. The study manager, under the supervision of the study statistician, will maintain control of the randomization matrix to ensure unbiased group assignment during the randomization process. Although this is not a blinded study, the PI's and health coaches will not be involved in any part of the randomization to further ensure an unbiased process.

***Inclusion criteria:*** i) aged 18-45 years, ii) "at-risk" weight defined as  $>7\%$  weight gain in the prior 2 years, overweight (BMI 25-29.9) OR class I obesity (BMI 30-32.49) iii) SMI diagnosis with  $<5$  years treatment,

iv) receiving case management services in one of the two CMHC study sites v) University of California, San Diego Brief Assessment of Capacity to Consent (UBACC) score  $> 14$  vi) not taking weight loss medications or participating in another behavioral weight loss intervention, vii) mild to moderate psychiatric symptom severity as measured by the Clinical Global Impression – Severity scale viii) willing and able to provide written informed consent.

**Exclusion criteria:** i) taking weight loss medications or participating in another behavioral weight loss intervention, ii) documented diagnosis of diabetes and/or treatment with an antidiabetes agent (diagnoses of hypertension and hyperlipidemia acceptable), iii) UBACC score  $\leq 14$ , iv) acute suicidality at time of screening, v) unwilling or unable to provide written informed consent.

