### **Detailed Study Procedures:**

*Literacy & facility with mobile technology:* Each participant will be administered the Rapid Estimate of Adult Literacy in Medicine-Short Form or REALM-SF to estimate literacy and the University of California, San Diego Brief Assessment of Capacity to Consent or UBACC to establish understanding of the study and active treatment. The accessibility of and ability to use mobile devices is necessary for participation in this study.

Thus, prior to randomization, all participants will undergo one week of text messaging to ensure that they are able to receive and appropriately respond to text messages.

**Rationale for study length of 24 weeks:** In the MEAC study, the PI's demonstrated rapid onset weight gain within 12 weeks of initial antipsychotic exposure. Although weight gain, particularly that associated with medications, can be rapid, it is generally well accepted that meaningful weight loss efforts may take longer than 12 weeks. We plan for a fully powered future study with an active treatment phase that is 6 months in duration, similar to currently running Phase 3 clinical trials (cite Alkermes). Published weight loss intervention studies in mentally ill youth and adults of 4 months in duration show separation from control groups. For the proposed study, our primary goal is to establish feasibility, tolerability and target engagement during active treatment, as well as to evaluate engagement and outcomes following a text-only 12-week extension.

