**Multidimensional Scale of Perceived Social Support.** This 12-item scale is designed to measure perceived social support from three sources: Family, Friends, and a Significant Other. Scores < 3 will prompt use of interpersonal effectiveness materials in coaching sessions (identifying relationships that support health behavior change, shoring up interpersonal effectiveness skills).

**Clinical Global Impression Scale.** The CGI was developed for use in NIMH-sponsored clinical trials to provide a brief, stand-alone clinical assessment of the patient's global functioning, taking into account the patient's history, psychosocial circumstances, symptoms, behavior, and the impact of the symptoms on ability to function.

**Medication Reconciliation & Compliance:** Our group has developed a medication log and reconciliation form to track medication compliance and changes during study participation. Participants will be asked at each in-person health coaching visit to update their medication list, which will then be reconciled with the case manager, physician and pharmacy.

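### Medication changes are logged but play no part in the weight analysis; the plan needs a baseline antipsychotic covariate, a table by arm and one supportive sensitivity analysis

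*SAP*

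**What the plan says.** The SAP's analytic plan states "The primary outcome for the present study will be weight change". For the analysis, "we will use a repeated-measures mixed model to look at trajectory over study course with a time x treatment interaction estimating the treatment effect". The same model appears in the protocol under *Data Analysis/Statistical Considerations*. No medication term is named in either place.

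The protocol's *Medication Reconciliation & Compliance* paragraph says "Our group has developed a medication log and reconciliation form to track medication compliance and changes during study participation". The list is updated at coaching visits and checked with the case manager, physician and pharmacy. The only analysis that uses any of this is in the exploratory paragraph: "Exploratory analyses will also evaluate how mental health self-efficacy and psychotropic medication compliance impact iOTA treatment compliance/engagement". That concerns compliance; recorded changes have no named use.

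The protocol's *Rationale for study length of 24 weeks* says that in an earlier study "the PI's demonstrated rapid onset weight gain within 12 weeks of initial antipsychotic exposure". The Aim 3 exclusion criteria bar people "taking weight loss medications or participating in another behavioral weight loss intervention", and also those treated with an antidiabetes agent. These are entry criteria. Neither the analysis sections nor *Participant Withdrawal* says how weights are treated if such a drug begins after randomisation.

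**The concern.** The investigators name a drug class that moves the primary outcome, collect data on changes in it, and then leave those data out of the analysis of that outcome. Eligibility makes this relevant: participants have had less than five years of treatment, and a gain above 7% in the prior two years is one route into the trial. Follow-up is long enough for medication to change, with weight taken at up to 10 visits over 9 months.

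Two things are at stake. The first is precision: in a comparison of 40 with 20, weight variation due to medication widens an already wide interval, and a baseline covariate could remove some of it. The second is interpretation: the trial is not blinded, so prescribing could come to differ by arm. Without a table of changes by arm, a reader could not tell whether that had happened. The SAP says the arm differences will inform the design of the next trial, so both matter beyond this pilot.

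**Working it through.** **What the documents supply.** The SAP says "We have chosen a 2:1 randomization ratio with a total sample of 60 subjects", which gives 60 × 2/3 = 40 and 60 × 1/3 = 20. It gives no SD, effect size, power or dropout figure, and no rate or weight effect of medication change, so there is no figure of the plan's own to reproduce. The ranges below are assumptions for illustration only: SD of weight change apart from medication changes, 4 to 8 kg; weight effect of a change, m = 2 to 5 kg; proportion with a change, p = 10% to 30%.

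**Precision of the arm difference.**
- √(1/40 + 1/20) = √0.075 = 0.274.
- SE = SD × 0.274 = 1.10 kg (SD 4), 1.64 kg (SD 6), 2.19 kg (SD 8).
- 95% half-width = 1.96 × SE = 2.15, 3.22 and 4.29 kg.

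**Changes unrelated to arm.** The expected shift is m × (p − p) = 0.
- Chance imbalance in the proportion has SD √(p(1−p)) × 0.274 = 0.082 (p = 0.1), 0.110 (p = 0.2), 0.125 (p = 0.3). Times 2 to 5 kg, this is 0.16 to 0.63 kg.
- Like for like, its 95% range is ±1.96 × (0.16 to 0.63), about ±0.3 to 1.2 kg, to be set against the half-widths above, not against one SE.
- It is not additional to the SE that the trial would estimate. Example with SD 6, p = 0.3, m = 5: total SD = √(36 + 0.21 × 25) = 6.42, and SE = 6.42 × 0.274 = 1.76 kg. Combining the parts gives the same: √(1.64² + 0.63²) = 1.76 kg.
- Over the full ranges, √(SD² + p(1−p)m²)/SD runs from 1.003 to 1.152, so the residual SD rises by 0.3% to 15%.
- A simulation of 40,000 null trials per setting (SD 6, two-sample t-test at two-sided 0.05, 20% changing in each arm) rejected in 5.1% (m = −3 kg) and 5.0% (m = −5 kg).

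**Changes that differ by arm.** Shift = m × difference in rates.
- 10 points: 0.2 to 0.5 kg. 20 points: 0.4 to 1.0 kg.
- Simulated with a weight-lowering drug in 10% of iOTA and 30% of control: the contrast moves 0.6 kg (m = −3) or 1.0 kg (m = −5) against iOTA, and the null is rejected in 6.7% or 9.1%. Reversing the rates would favour iOTA.

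**Baseline use.** The documents do not say how many participants take an antipsychotic at entry, so the precision gained from adjusting for it cannot be sized.

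**Model cost.** A yes/no covariate with its interaction with linear time adds 1 + 1 = 2 parameters. A three-level factor would add 2 + 2 = 4 with linear time, or 2 + 2 × 9 = 20 with ten categorical visits.

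**The case against.** A reader might infer that medication changes will be mistaken for a treatment effect, or that the contrast is confounded. The documents do not support that. Allocation is randomised, so changes unrelated to arm leave the expected contrast untouched. Systematic bias needs unequal change rates; none is shown, and the direction is open. If assignment itself alters prescribing, a comparison that keeps all weights properly includes that consequence.

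A reader might also infer that chance imbalance rivals the treatment effect. The documents give no effect size to compare it with. They also give no rate of recent antipsychotic starts, and the protocol's statement concerns initial exposure, not switching. Weight gained before entry is already in the baseline.

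Nor do the documents show that changes reported at remote visits would be lost. The reconciliation paragraph says in-person, but it sits under a heading that covers each study visit, and later reconciliation could pick up earlier changes. This is a wording inconsistency.

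The log is described as covering changes during participation, so start dates before baseline cannot be assumed. Finally, the SAP places testing and effect-size estimation outside its scope and plans to explore variables such as age, gender, race and ethnicity.

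All of this stands, and it limits the size of the point. It does not remove it. The SAP still makes weight change primary, calls the interaction the treatment effect and carries arm differences forward to the next design. Its list of factors to explore does not name medication, nor do the seven feasibility items to be related to BMI and self-efficacy.

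**Conclusion.** The gap is real and modest. Medication data enter no stated analysis of weight, recorded changes have no stated use, and weights after a relevant change have no handling rule. What follows from the documents is avoidable noise and an unchecked possibility of arm-related change, not a demonstrated bias.

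On the assumed ranges, unrelated changes raise the residual SD by 0.3% to 15%. Arm-related changes of 10 to 20 points would shift the contrast by 0.2 to 1.0 kg in either direction, which is smaller than the 95% half-width of 2.15 to 4.29 kg. Every kg figure rests on those assumptions. The change is worth making because it is cheap and the results will shape a later trial.

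**What to change.** In the SAP's planned primary and secondary analysis, and in the matching protocol section:

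1. Add baseline antipsychotic use (yes/no, from the baseline medication list), with its interaction with linear time, to the weight and BMI model. Use a recent-start category only if start dates are recorded at the first log entry.
2. State that the main analysis keeps all weights regardless of later medication changes.
3. Tabulate by arm the starts of weight-loss or antidiabetes drugs, and antipsychotic starts, stops and switches.
4. Add one sensitivity analysis that excludes weights after such a change. Label it supportive, because it conditions on events after randomisation that assignment may have influenced. Do not enter later medication as an ordinary covariate, for the same reason.

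In the protocol, reconcile the in-person wording of *Medication Reconciliation & Compliance* with the remote visits allowed under *Randomization of participants* and with its own section heading.

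The cost is about two model parameters in a 60-person pilot, given a binary covariate and linear time, plus a little analysis work. Nobody's care changes.
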